6.2 APPENDIX 2 - LIST OF EXAMPLE INHIBITORS AND INDUCERS OF CYP3A4

Strong Inhibitors (≥ 5 -fold increase in AUC or $>80\%$ decrease in oral clearance):

Boceprevir
Clarithromycin
Conivaptan
Grapefruit juice
Indinavir
Itraconazole
Ketoconazole
Lopinavir/ritonavir
Mibepradil
Nefazodone
Nelfinavir
Posaconazole
Ritonavir
Saquinavir
Telaprevir
Telithromycin
Voriconazole

Strong Inducers ($\geq 80\%$ decrease in AUC):

Avasimibe
Carbamazepine
Phenytoin
Rifampin
St John's wort

Note: This list is not all-inclusive. Please refer to the following website for further guidance:
<http://www.fda.gov/drugs/developmentapprovalprocess/developmentresources/druginteractionslabeling/ucm093664.htm>

6.3 APPENDIX 3 - INFUSION SITE ASSESSMENT

The investigator will assess the degree of reaction at the infusion site at scheduled time points during the study using the following rating scale:

Adverse Events of Interest	Mild (Grade 1)	Moderate (Grade 2)	Severe (Grade 3)	Potentially Life Threatening (Grade 4)
Injection site adverse events				
Pain	Does not interfere with activity	Repeated use of non-narcotic pain reliever for >24 hours or interferes with activity	Any use of narcotic pain reliever or prevents daily activity	Emergency room visit or hospitalization
Tenderness	Mild discomfort to touch	Discomfort with movement	Significant discomfort at rest	Emergency room visit or hospitalization
Erythema/redness*	2.5 – 5 cm	5.1 – 10 cm	>10 cm	Necrosis or exfoliative dermatitis
Induration/swelling**	2.5 – 5 cm and does not interfere with activity	5.1 – 10 cm or interferes with activity	>10 cm or prevents daily activity	Necrosis

* In addition to grading the measured local reaction at the greatest single diameter, the measurement should be recorded as a continuous variable.

** Induration/swelling should be evaluated and graded using the functional scale as well as the actual measurement.

**6.4 APPENDIX 4: SECOND SYMPOSIUM ON THE
DEFINITION AND MANAGEMENT OF ANAPHYLAXIS:
SUMMARY REPORT—SECOND NATIONAL INSTITUTE
OF ALLERGY AND INFECTIOUS DISEASE/FOOD
ALLERGY AND ANAPHYLAXIS NETWORK SYMPOSIUM**

Second symposium on the definition and management of anaphylaxis: Summary report—Second National Institute of Allergy and Infectious Disease/Food Allergy and Anaphylaxis Network symposium can be accessed at the following website link:

<http://www.jacionline.org/article/S0091-6749%2805%2902723-5/pdf>

Clinical criteria for diagnosing anaphylaxis are presented in Table 6.4.

Table 6-4 Clinical Criteria for Diagnosing Anaphylaxis

Anaphylaxis is highly likely when any one of the following 3 criteria are fulfilled:

1. Acute onset of an illness (minutes to several hours) with involvement of the skin, mucosal tissue, or both (eg, generalized hives, pruritus or flushing, swollen lips-tongue-uvula) AND AT LEAST ONE OF THE FOLLOWING:
a. Respiratory compromise (eg, dyspnea, wheeze-bronchospasm, stridor, reduced PEF, hypoxemia)b. Reduced BP or associated symptoms of end-organ dysfunction (eg, hypotonia [collapse], syncope, incontinence)2. Two or more of the following that occur rapidly after exposure to a likely allergen for that patient (minutes to several hours):
a. Involvement of the skin-mucosal tissue (eg, generalized hives, itch-flush, swollen lips-tongue-uvula)b. Respiratory compromise (eg, dyspnea, wheeze-bronchospasm, stridor, reduced PEF, hypoxemia)c. Reduced BP or associated symptoms (eg, hypotonia [collapse], syncope, incontinence)d. Persistent gastrointestinal symptoms (eg, crampy abdominal pain, vomiting)3. Reduced BP after exposure to known allergen for that patient (minutes to several hours):
a. Infants and children: low systolic BP (age specific) or greater than 30% decrease in systolic BP¹b. Adults: systolic BP of less than 90 mm Hg or greater than 30% decrease from that person's baseline

Abbreviations: BP, blood pressure; PEF, peak expiratory flow.

¹ Low systolic blood pressure for children is defined as less than 70 mm Hg from 1 month to 1 year, less than (70 mm Hg + [2 × age]) from 1 to 10 years, and less than 90 mm Hg from 11 to 17 years.

13. INTERIM ANALYSIS	41
14. REFERENCE.....	42
15. TABLE OF CONTENTS: TABLES, LISTINGS AND FIGURES.....	43

List of Abbreviations

ADA	anti-drug antibody
Ae	total amount of drug excreted in urine
AE	adverse event
AUC	area under curve
BID	twice daily
BLQ	below the limit of quantification
BMI	body mass index
CI	confidence interval
CL	total body clearance
CL _r	renal clearance
CSR	clinical study report
CTCAE	Common Terminology Criteria for Adverse Event
CV	coefficient of variation
eCRF	electronic case report form
DLT	dose limiting toxicity
ECG	electrocardiogram
EOS	end of study
FA	final-extent of platelet aggregation
IV	intravenous
LTA	light transmittance aggregometry
MA	maximal-extent of platelet aggregation
NAb	neutralizing antibody
PD	pharmacodynamics
PK	pharmacokinetics

PRU	P2Y ₁₂ reaction units
PT	preferred term
QTcB	Bazett's-corrected QT interval
QTcF	Fridericia-corrected QT interval
Rsq	regression coefficient (R squared)
SAE	serious adverse event
SAS	statistical analysis software
SD	standard deviation
SOC	system organ class
SRC	safety review committee
$t_{1/2}$	terminal elimination half-life
TEAE	treatment-emergent adverse event
T_{max}	time to reach the maximum plasma concentration
VASP	Vasodilator-stimulated phosphoprotein
V_d	volume of distribution
λ_z	terminal phase rate constant

1. Introduction

MEDI2452 (PB2452) is a specific and selective neutralizing antibody fragment that binds ticagrelor and AR-C124910XX, the major active circulating ticagrelor metabolite, with high affinity. MEDI2452 (PB2452) is intended to reverse the antiplatelet effects of ticagrelor in patients who experience major bleeding or who require urgent surgery or intervention, serious but rare conditions that represent an unmet medical need.

This is the first-in-human study with MEDI2452 (PB2452) and is designed to provide initial safety, tolerability, pharmacokinetics (PK), and pharmacodynamics (PD) data regarding MEDI2452 (PB2452) for future clinical studies.

This statistical analysis plan (SAP) reflects the protocol amendment 5 dated 03 August, 2018.

2. Objectives

2.1. Primary

The primary objectives of this study are:

- To evaluate the safety and tolerability of single ascending intravenous (IV) doses of MEDI2452 (PB2452) with or without ticagrelor
- To evaluate the effectiveness of single ascending doses of MEDI2452 (PB2452) dose on ticagrelor antiplatelet activity using light transmittance aggregometry (LTA)

2.2. Secondary

The secondary objectives of the study are:

- To determine the PK of ascending doses of IV MEDI2452 (PB2452) in the presence and absence of ticagrelor
- To determine the PK of ticagrelor and its active metabolite AR-C124910XX in the presence and absence of MEDI2452 (PB2452)

- To assess the effectiveness of a single IV MEDI2452 (PB2452) dose in reversing ticagrelor antiplatelet activity by measuring P2Y₁₂ reaction units (PRU) with VerifyNow™ P2Y₁₂ assay and platelet reactivity index (PRI) with vasodilator stimulated phosphoprotein (VASP) phosphorylation assay by enzyme-linked immunosorbent assay (ELISA)
- To evaluate the PK and PD of restarting a single dose of oral ticagrelor 24 hours after MEDI2452 (PB2452) administration if a sixth dose of ticagrelor is given
- To evaluate the immunogenicity potential of MEDI2452 (PB2452)

2.3. Exploratory

The exploratory objective is to evaluate the effect of MEDI2452 (PB2452) on the PK profile of unbound ticagrelor and unbound AR-C124910XX plasma concentrations.

3. Investigational Plan

This is a Phase 1, first-in-human, randomized, double-blind, placebo-controlled, single ascending dose, sequential group study to evaluate the safety, tolerability, PK, and PD of MEDI2452 (PB2452) with and without ticagrelor pretreatment when administered to healthy male and female subjects. All references to study drug within this statistical analysis plan (SAP) apply to MEDI2452 (PB2452) or matching placebo.

This study will have up to 10 cohorts and up to a total of 68 subjects with either 4 or 8 subjects in each cohort. The starting dose of MEDI2452 (PB2452) will be 100 mg and the planned doses for subsequent cohorts are 300, 1000, 3000, 9000, and 18000 mg. Other intermediate doses may also be tested but will not exceed 1800 mg.

The study will consist of a screening period (Days -45 to -4), check-in/pretreatment (Day -3 to Day -1), an in-house treatment period (Days 1 through 3 [Cohorts 1 through 8] or 4 [Cohorts 9 and 10]), and follow-up visits (Days 4, 7, and 28 [+2 days]). Subjects will receive an IV dose of study drug on Day 1.

On Day 1, subjects who meet all the inclusion criteria and none of the exclusion criteria will be randomly assigned to receive MEDI2452 (PB2452) or placebo in a ratio of 3:1 in all treatment cohorts as described below and as summarized in [Table 3-1](#).

Table 3-1 Summary of Treatment per Cohort

Cohort	Pre-MEDI2452 (PB2452) ticagrelor dosing to steady state (180 mg + 90 mg bid for 5 doses total)	MEDI2452 (PB2452) Dose (mg)	Number of subjects MEDI2452 (PB2452):placebo
1		100	3:1
2		300	3:1
3		1000	3:1
4	180 mg + 90 mg bid	1000	6:2
5	180 mg + 90 mg bid	3000	6:2
6	180 mg + 90 mg bid	9000	6:2
7	180 mg + 90 mg bid	18000	6:2
8	180 mg + 90 mg bid	18000	6:2
9	180 mg + 90 mg bid	18000	3:1 or 6:2*
10	180 mg + 90 mg bid	18000	3:1 or 6:2*

Abbreviations: bid, twice daily.

*Initially the cohort size will be 4 subjects (3:1); if needed for confirmation of PK/PD an additional 4 subjects (3:1) will be randomized in that same cohort.

Cohorts 1 to 3:

For the initial cohort (Cohort 1), 4 healthy subjects will be randomly assigned in a 3:1 ratio of active treatment to placebo (3A:1P) to receive a single 100-mg IV dose of study drug over 30 minutes. For the second cohort (Cohort 2), 4 healthy subjects will be randomly assigned (3A:1P) to receive a single 300-mg IV dose of study drug over 30 minutes. For the third cohort (Cohort 3), 4 healthy subjects will be randomly assigned (3A:1P) to receive a 1000-mg IV dose of study drug over 30 minutes.

Cohorts 4 to 6:

[figure not shown]
Provided no safety concerns arise in Cohorts 1 through 3, 8 subjects in each of Cohorts 4 through 6 will be randomly assigned in a 3:1 ratio (6A:2P) to receive a single IV dose of study drug simultaneous with the 5th dose of ticagrelor pretreatment. For ticagrelor pretreatment, subjects will receive an oral loading dose of 180-mg ticagrelor in the morning (Day -2), followed by 90-mg ticagrelor orally every 12 hours for 4 additional doses, prior to administration of a single IV dose of study drug simultaneous with the 5th ticagrelor dose (Day 1). Subjects in each of Cohorts 4 through 6 will receive ticagrelor pretreatment, as described above, and a single IV dose of 1000, 3000, or 9000 mg of study drug, respectively, over 30 minutes. Cohorts 4 through 6 will be dosed sequentially following the safety and dose-escalation assessment of each preceding dose cohort.

Cohorts 7 to 10:

For Cohorts 7 to 10, following ticagrelor pretreatment, subjects will be randomly assigned in a 3:1 ratio (3A:1P or 6A:2P) to receive a single IV dose of study drug. The IV infusion of study drug will be initiated 2 hours after the 5th ticagrelor dose. The duration of the infusion will be determined upon analysis of data from prior cohorts, and will range between 30 minutes and 24 hours. Total doses to be administered in these cohorts will be determined based upon analysis of data from prior cohorts, and will be within the range of 9000-18000 mg.

The overall Study design is presented in [Figure 3-1](#).

Figure 3-1 Study Flow Diagram

Schedule of Events is presented in [Table 3-2](#).

Table 3-2 Schedule of Events

Procedure	Screening	Check-in/ Pretreatment			Treatment				Follow -up ^a	EOS ^a
		-45 to -4	-3	-2	-1	1	2	3	4/FU	
Study Day(s)	-45 to -4								7	28 (+2 days)
Informed consent	X									
Inclusion/exclusion criteria	X	X ^c			X ^d					
Demographics	X									
Medical history	X									
Urine drug screen (includes cotinine)	X	X ^c			X ^d					
Urine alcohol	X	X ^c			X ^d					
Serum pregnancy test	X	X ^c			X ^d					X
Serology testing	X									
Admission to clinic		X ^c			X ^d					
Physical examination ^e	X	X ^c			X ^d			X		X X
Vital sign measurements ^f	X	X ^c			X ^d	X	X	X	X	X X
12-lead electrocardiogram ^g	X					X	X	X		X X
Cardiac telemetry monitoring ^h		X			X	X	X	X		
Clinical laboratory testing	X	X ^c			X ^d			X		X X
Randomization						X				
Drug administration										
Ticagrelor			X ⁱ	X ⁱ	X ⁱ					
MEDI2452 (PB2452)/Placebo ^k					X					
PK blood sampling ^l										
Plasma MEDI2452 (PB2452) ^l					X	X	X	X ^{aa}	X	X
Plasma ticagrelor/AR-C124910XX ^l					X	X	X ^x	X		
Free plasma ticagrelor/AR-C124910XX ^l					X	X	X ^x	X		
PK urine sampling ^q			X		X	X	X			
PD sampling (LTA/PRU/VASP) ^r			X		X	X	X			
Infusion site assessment ^t					X	X	X	X	X	
Serum immunogenicity		X ^c		X ^d					X	X ^w
Adverse events		X ^c	X ^c	X	X	X	X	X	X	X
Discharge from clinic								X ^u	X	

Abbreviations: BID, twice daily; EOS, end-of-study; FU, follow-up; LTA, light transmittance aggregometry; PD, pharmacodynamic; PK, pharmacokinetic; PRU, P2Y₁₂ reaction units; VASP, vasodilator stimulated phosphoprotein.

- ^a Follow-up visits will be conducted as outpatient.
- ^c Cohorts 4 through 10 only.
- ^d Cohorts 1 through 3 only.
- ^e Full physical examination (including height, weight, and body mass index calculation) will be performed at screening and Day 28 only. Brief physical examinations will be performed at all other time points.
- ^f Vital sign measurements (systolic and diastolic blood pressures, oral body temperature, respiratory rate, and heart rate) will be collected at screening, check-in, before dosing (30 minutes prior to the initiation of the study drug infusion) and at 0.5, 0.75, 1, 2, 4, 8, and 24 hours after the initiation of the study drug infusion, and at 30, 36, 42, and 48 hours after the initiation of the study drug infusion and on Days 4, 7, and 28. Starting with the 1 hour after initiation of the study drug timepoint for the collection of vitals a ±5 minute window will be permitted. During the initial 30 minutes of study drug infusion, systolic and diastolic blood pressures and heart rate will be collected every 5 minutes.
- ^g Electrocardiograms will be obtained in triplicate for all subjects at screening, before dosing (within 1 hour prior to the initiation of the study drug infusion) and at 1 (±10 minutes), 4 (±10 minutes), 5 (±10 minutes), 24 (±30 minutes), and 48 hours (±30 minutes) after the initiation of the study drug infusion and on Days 7 and 28.
- ^h Cardiac telemetry monitoring will begin on Day -1 approximately 12 hours prior to the initiation of the study drug infusion (Hour 0) and will continue until the subject is discharged from the clinical site for Cohorts 1-10. For Cohorts 4-10, cardiac telemetry monitoring will begin on Day-3 (check in) approximately 12 hours prior to the first dose of Ticagrelor and will be removed once dosed with the initial dose of Ticagrelor.
- ⁱ For Cohorts 4 through 6 only: Beginning in the morning on Day -2, ticagrelor will be administered as a single oral dose of 180 mg, followed by 90 mg every 12 hours for 4 additional doses through Hour 0 (i.e., 5 total doses of ticagrelor). For Cohorts 7 through 10 only: Beginning in the morning on Day -2, ticagrelor will be administered as a single oral dose of 180 mg, followed by 90 mg every 12 hours for 4 additional doses through to Hour -2 (two hours prior to dosing at Hour 0) (i.e., 5 total doses of ticagrelor).
- ^k For all cohorts: MEDI2452 (PB2452) or placebo will be administered at Hour 0 of Day 1.
- ^l For timing of pharmacokinetic plasma samples for each cohort, refer to [section 3.5.1](#) of the protocol.
- ^q For Cohorts 4 through 10 only: Urine samples for PK analysis of ticagrelor and AR-C124910XX concentrations will be collected before dosing (within 60 minutes prior to the first ticagrelor dose on Day -2), and 0 to 6, 6 to 12, 12 to 24 and 24 to 48 hours after the initiation of the study drug infusion.
- ^r For timing of pharmacodynamic samples for each cohort, refer to [section 3.5.2](#) of the protocol.
- ^t Infusion site assessments will be performed for all subjects within 15 minutes prior to the initiation of the study drug infusion (Hour 0), and at 1, 3, 24, 48, and 72 hours after initiation of the study drug infusion and on Day 7.
- ^u For Cohorts 1 through 8 only.
- ^w Subject may be required to return to collect additional follow-up samples should the sample collected at day 28 test positive for anti-drug antibody development. These visits may be done approximately 3 months after their final visit and approximately every 6 months thereafter or until their levels return to baseline.
- ^x For Cohorts 4-10: Blood samples for determination of plasma ticagrelor and AR-C124910XX AND unbound plasma ticagrelor and AR-C124910XX will be collected 48 hours after the initiation of the study drug infusion.

^{aa}Omitted for Cohorts 7-10.

Note: Footnotes b, j, m, n, o, p, s, v, y, z are intentionally omitted.

4. General Statistical Considerations

All statistical analyses will be conducted using statistical analysis system SAS® software (SAS Institute, Cary, NC USA) Version 9.3 or higher (version to be delineated in the clinical study report [CSR]). All tables and data listings will appear in landscape format employing Courier New 9-point font.

4.1. General Data Presentation Rules

All data will be provided in individual by-subject listings.

Data from subjects excluded from an analysis population will be presented in the data listings but not included in the calculation of summary statistics.

Data from subjects receiving placebo will be pooled across cohorts for all presentations.

Unless otherwise noted, the following treatment groups will be used in summaries:

- 100 mg PB2452 (C1)
- 300 mg PB2452 (C2)
- 1000 mg PB2452 (C3)
- Placebo C1-C3
- 1000 mg PB2452 (C4)
- 3000 mg PB2452 (C5)
- 9000 mg PB2452 (C6)
- Placebo C4-C6
- 18000 mg PB2452 (C7)
- 18000 mg PB2452 (C8)
- 18000 mg PB2452 (C9)

- 18000 mg PB2452 (C10)
- Placebo C7-C10
- All Placebo (for safety summaries only)
- All PB2452 (for safety summaries only)
- All subjects

where 'C' means 'Cohort'.

Demographic data, baseline characteristics, adverse events (AEs), laboratory tests, vital signs, 12-lead electrocardiogram (ECG) measurements, and subject disposition will be summarized descriptively.

Unless otherwise noted, the summary of the continuous variables will include the number of subjects with non-missing data (n), mean, standard deviation (SD), median, minimum, and maximum. Categorical variables will be summarized descriptively by their counts and associated percentages. Percentages will be calculated using the number of subjects within a summary group as the denominator.

Minimum and maximum values will be presented as the same precision as the original value. Means and medians will be presented as 1 decimal place greater than the precision of the original value. Standard deviations will be presented as 2 decimal places greater than the precision of the original value. Percentages for summarizing categorical data will be presented with 1 decimal place. If the percentage value is less than 0.1, then "<0.1" will be displayed.

Unless specified otherwise, baseline for safety analyses is defined as the last non-missing measurement (including repeated and unscheduled measurements) prior to the first study drug administration; baseline for PD analyses is defined as the last non-missing measurement (including repeated and unscheduled measurements) prior to the first ticagrelor administration.

Listings will be sorted by treatment group and subject identifier.

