simultaneous with the 5th ticagrelor dose (Day 1). Subjects in each of Cohorts 4 through 7 will receive ticagrelor pretreatment, as described above, and a single IV dose of 1000, 3000, 9000, or 18000 mg of MEDI2452 (PB2452), respectively, or placebo over 30 minutes. Cohorts 4 through 7 will be dosed sequentially following the safety and dose-escalation assessment of each preceding dose cohort.

Cohorts 8 and 9:

For the final 2 dose cohorts (Cohorts 8 and 9), following ticagrelor pretreatment, subjects will be randomly assigned (6A:2P) to receive a single IV dose of 9000 or 18000 mg of MEDI2452 (PB2452), respectively, or placebo, and will also receive an additional single oral dose of 180-mg ticagrelor 24 hours after the initiation of the MEDI2452 (PB2452) or placebo infusion. Cohort 8 may be initiated following the safety and dose escalation assessment of Cohort 6 (9000-mg MEDI2452 [PB2452]), and Cohort 9 may be initiated following the safety and dose escalation assessment of Cohort 7 (18000-mg MEDI2452 [PB2452]).

Cohort	Pre-MEDI2452 (PB2452) ticagrelor dosing to steady state (180 mg + 90 mg bid for 5 doses total)	MEDI2452 (PB2452) Dose (mg)	Post-MEDI2452 (PB2452) Ticagrelor (180 mg) 24 hours following MEDI2452 (PB2452) or placebo	Number of subjects MEDI2452 (PB2452):placebo
1		100		3:1
2		300		3:1
3		1000		3:1
4	180 mg + 90 mg bid	1000		6:2
5	180 mg + 90 mg bid	3000		6:2
6	180 mg + 90 mg bid	9000		6:2
7	180 mg + 90 mg bid	18000		6:2
8	180 mg + 90 mg bid	9000	180 mg	6:2
9	180 mg + 90 mg bid	18000	180 mg	6:2

Abbreviations: BID, twice daily

Dosing for Cohort 1 (first exposure of MEDI2452 [PB2452] in humans) will proceed with two sentinel subjects initially randomly assigned to receive a single IV dose of MEDI2452 (PB2452) or placebo. Blinded safety data from the sentinel subjects up to 24-hours following the MEDI2452 (PB2452) or placebo dose will be reviewed by the investigator before the remaining 2 subjects in Cohort 1 are dosed. The remaining subjects will be dosed at least 24 hours after the sentinel subjects. Additionally, dosing for Cohort 4 (first exposure of the combination of MEDI2452 [PB2452] with ticagrelor in humans) will proceed with 2 sentinel

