8.2. Clinical Laboratory Evaluations

Blood samples for laboratory safety tests (hematology, coagulation and serum chemistry) and urine samples for urinalysis will be collected at Screening, Day -3 (Cohorts 4 through 10 only), Day -1 (Cohorts 1 through 3 only), Day 3 (Cohorts 1 through 8 and 10 only), Day 4 (Cohort 9 only if a 6th dose of ticagrelor was given on Day 2), Day 7, and Day 28/EOS.

Serology testing will be performed at Screening.

Urine drug, alcohol screen, and Hemoglobin A1C for diabetic patients, will be performed at Screening, Day -3 (Cohorts 4 through 10 only), and Day -1 (Cohorts 1 through 3 only).

Serum pregnancy test for female subjects will be performed at Screening, Day -3 (Cohorts 4 through 10 only), Day -1 (Cohorts 1 through 3 only), and Day 28/EOS.

Stool occult blood test will be performed at Screening for Cohort 10 only.

The following clinical laboratory assessments will be performed:

Hematology: Hematocrit, hemoglobin, mean corpuscular hemoglobin, mean corpuscular hemoglobin concentration, mean corpuscular volume, platelet count, red blood cell count, and total and differential leukocyte count

Coagulation: Activated partial thromboplastin time, international normalized ratio, partial thromboplastin time, and prothrombin time

Serum Chemistry: Alanine aminotransferase, albumin, alkaline phosphatase, aspartate aminotransferase, bicarbonate, bilirubin (total and direct), blood urea nitrogen, calcium, chloride, cholesterol (total, high-density lipoprotein, and calculated low-density lipoprotein), creatine phosphokinase, creatinine, gamma-glutamyltransferase, globulin, glucose, lactate dehydrogenase, magnesium, phosphorus, potassium, sodium, thyroid stimulating hormone (Screening only), total protein, triglycerides, and uric acid

Urinalysis: Appearance, bilirubin, color, glucose, ketones, leukocyte esterase, reflex microscopy (performed if dipstick is positive for protein or blood value of 1+ or greater; and includes bacteria, casts, crystals, epithelial cells, red blood cells, and white blood cells), nitrites, occult blood, pH, protein, specific gravity, turbidity, and urobilinogen

Serology: Hepatitis B surface antigen, hepatitis C virus antibody, and human immunodeficiency virus types 1 and 2 antibodies

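### If Cohort 9 receives the sixth ticagrelor dose that the SAP leaves open, the Placebo C7-C10 column mixes five- and six-dose subjects after 24 h, and no rule separates them

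*SAP*

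**What the plan says.** SAP 4.1 sets the general rule: "Data from subjects receiving placebo will be pooled across cohorts for all presentations". The list of treatment groups below it narrows that rule. Placebo appears as C1-C3 (no ticagrelor), C4-C6 (fifth dose together with the infusion) and "Placebo C7-C10" (fifth dose two hours before the infusion). The fully pooled column is restricted: "All Placebo (for safety summaries only").

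On the number of ticagrelor doses, the SAP does not speak with one voice:

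- Table 3-2, footnote i, gives Cohorts 7-10 "additional doses through to Hour -2 (two hours prior to dosing at Hour 0) (i.e., 5 total doses of ticagrelor"). The table has no Day 2 ticagrelor entry, and section 7.3 describes Cohorts 9 and 10 under one shared regimen without a sixth dose.
- The secondary objective in section 2.2 covers restarting ticagrelor "24 hours after MEDI2452 (PB2452) administration if a sixth dose of ticagrelor is given".
- The laboratory schedule in section 8.2 provides for "Day 4 (Cohort 9 only if a 6th dose of ticagrelor was given on Day 2").

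Section 11.1 summarises PD data by treatment group at each time point, so the pooled placebo column is what the reader sees beside each PB2452 cohort.

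**The concern.** A primary objective is the effect of PB2452 on ticagrelor antiplatelet activity. A placebo column serves that objective only if its subjects had the same ticagrelor dosing as the PB2452 cohort beside it. The list in 4.1 observes this principle for ticagrelor use and for the timing of the fifth dose, but it has no provision for a sixth dose. C7-C10 is the only placebo group in which five- and six-dose subjects could be mixed.

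The mix would work in two directions. Re-dosed placebo subjects are expected to be more inhibited, so the pooled mean would be too low as a control for the cohorts not restarted, and PB2452 reversal there would look larger or longer-lasting. For restarted PB2452 Cohort 9 the pooled mean would be too high, because most of the pool was not restarted. That comparison bears on the secondary objective about restarting ticagrelor.

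**Working it through.** **Cohort sizes.** SAP Table 3-1 gives Cohorts 1-3 four subjects each and Cohorts 4-8 eight each. For Cohorts 9 and 10 it says: "Initially the cohort size will be 4 subjects (3:1); if needed for confirmation of PK/PD an additional 4 subjects (3:1) will be randomized". The SAP's stated maximum is reproduced: 3 × 4 + 7 × 8 = 68. With Cohorts 9 and 10 left at four, the total is 12 + 40 + 8 = 60.

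**Placebo counts.** C1-C3: 3 × 1 = 3. C4-C6: 3 × 2 = 6. C7 and C8: 2 each. C9 and C10: 1 or 2 each. Placebo C7-C10 therefore has 2 + 2 + (1 or 2) + (1 or 2) = 6 to 8 subjects.

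**Sampling after 24 h (SAP 11.1).** Cohorts 7-8 have a PD sample at 48 h only. Cohorts 9-10 have samples at 28, 36 and 48 h. At 28 and 36 h the pooled PD column therefore holds only Cohort 9 and Cohort 10 placebo subjects.

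**Share re-dosed, if all Cohort 9 placebo subjects take a sixth dose.** At 48 h the share s is (C9 placebo) / (C7-C10 placebo). At 28 and 36 h it is (C9 placebo) / (C9 + C10 placebo).

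| C9, C10 placebo | Pool | s at 48 h | s at 28/36 h | Not re-dosed at 48 h |
|---|---|---|---|---|
| 1, 1 | 6 | 1/6 = 16.7% | 1/2 = 50% | 83.3% |
| 1, 2 | 7 | 1/7 = 14.3% | 1/3 = 33.3% | 85.7% |
| 2, 1 | 7 | 2/7 = 28.6% | 2/3 = 66.7% | 71.4% |
| 2, 2 | 8 | 2/8 = 25.0% | 2/4 = 50% | 75.0% |

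Placebo C4-C6 has 0 of 6 re-dosed.

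**Shift in the placebo mean.** Let D be the five-dose minus six-dose difference in percent-of-baseline aggregation at a given time. For cohorts not restarted, the pooled mean is low by s × D. For restarted PB2452 Cohort 9 it is high by (1 − s) × D. The documents give no D. Purely as an illustration, with assumed values:

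| Assumed D (points) | s × D at 48 h | s × D at 28/36 h |
|---|---|---|
| 20 | 2.9-5.7 | 6.7-13.3 |
| 40 | 5.7-11.4 | 13.3-26.7 |
| 60 | 8.6-17.1 | 20-40 |

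Conversely, a 5-point shift needs D = 5/s: 7.5 to 15 points at 28/36 h, and 17.5 to 35 points at 48 h. These times fall 4, 12 and 24 h after the sixth dose, and D need not be the same at each, so a row of the table should not be read across as one scenario.

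**Other summaries affected.** For ticagrelor and its metabolite, AUC0-48, Ae48 and CLr48 (SAP 10.1.2 and 10.2.2) have windows that span the sixth dose. Vital signs at 30, 36, 42 and 48 h are taken in every cohort, so the C7-C10 share there is also 14-29%. All Placebo has 3 + 6 + (6 to 8) = 15 to 17 subjects, of whom 1/16 = 6.3% to 2/16 = 12.5% would be re-dosed.

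**The case against.** The strongest reply is that the SAP does not schedule a sixth dose. Footnote i counts five doses, Table 3-1 has no column for ticagrelor after the infusion, and the SAP schedule states that several footnote letters are intentionally omitted, among them those that carried the sixth dose in the protocol of 01 Feb 2018. On that reading nothing is mixed. This stands as a limit: the problem is conditional. It does not remove it, because sections 2.2 and 8.2 still provide for the dose and 4.1 says nothing about what follows.

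A reader might infer from the opening sentence of 4.1 that all placebo subjects form one PK/PD control whatever their ticagrelor dosing. The group list does not support that.

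A reader might also take the protocol of 01 Feb 2018, where subjects in its Cohorts 8 and 9 "will also receive an additional single oral dose of 180-mg ticagrelor 24 hours after the initiation of the MEDI2452 (PB2452) or placebo infusion", and conclude that 4 of 12 ticagrelor-treated placebo subjects (33%) are re-dosed. The count is right for that protocol, but the SAP follows amendment 5 of 03 August 2018, so the figure is background only.

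Three further points have weight. The placebo comparisons are descriptive. By-subject listings and individual profiles would let a reader find re-dosed subjects, although the summary columns and mean curves would remain mixed. And section 11.2 summarises PD parameters by cohort, so it is not established that placebo is pooled for those; the SAP should say.

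**Conclusion.** The point holds in a confined, conditional form. It concerns Placebo C7-C10 only, only after 24 h, and only if Cohort 9 receives a sixth dose. In that case 14-29% of the pool at 48 h, and one third to two thirds of the placebo subjects with PD samples at 28 and 36 h, would be re-dosed. The column would then be unmatched for Cohort 10 at 28, 36 and 48 h, for Cohorts 7 and 8 at 48 h, and for PB2452 Cohort 9 itself, where 71-86% of the pool at 48 h was not restarted.

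The shares assume that every Cohort 9 placebo subject is re-dosed and that the 24 h sample is drawn before the dose; the SAP does not state that order. A reader might go further and quote a definite bias, up to 40 points. The documents do not support this: D is not given, may vary with time since re-dosing, and the 40-point figure needs D = 60 together with Cohort 9 expanded and Cohort 10 not. If no sixth dose is given, the shift is zero. A clarification before unblinding is warranted because it is cheap and bears on both the primary PD objective and the restart objective.

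**What to change.** First, reconcile SAP sections 2.2 and 8.2 with the five-dose schedule in Table 3-2, footnote i, so that the SAP states plainly whether a sixth dose is part of Cohort 9.

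If it remains possible, add to SAP 4.1:

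> If a sixth ticagrelor dose is given in Cohort 9, PK, PD and time-point safety data collected after that dose, and PK/PD parameters whose window extends past it, are excluded from Placebo C7-C10 and shown in a separate Placebo C9 (re-dosed) column beside PB2452 C9. With n = 1-2, individual values are shown.

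Also state in 11.2 whether placebo PD parameters are pooled or shown by cohort.

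The cost is a short rule and one column, used only if the dose is given. After 24 h the pool falls from 6-8 subjects to 5 or 6 (2 + 2 + 1 or 2). At 28 and 36 h only the 1 or 2 Cohort 10 placebo subjects remain, and the re-dosed column also has 1 or 2. With one subject there is no SD, hence the individual values. A very small matched control is still easier to interpret than a somewhat larger mixed one.
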